# **Protocol**

### **Abstract**

This is a trial of an FDA-approved treatment for Major Depressive Disorder (MDD), computer-augmented cognitive behavioral therapy (CCBT), to examine novel potential neural circuit biomarkers of treatment response rather than to test efficacy. We will enroll 60 subjects, 18-60 years, who are seeking treatment for a current episode of Major Depressive Disorder. We also will enroll 40 healthy controls of a similar age/sex distribution. MDD subjects will be scheduled to receive CCBT at the first available appointment; all will be scheduled within 4 weeks. All subjects will have an fMRI at baseline; MDD subjects will have an fMRI after treatment. MDD subjects scheduled to start CCBT treatment after 3 weeks will complete an additional fMRI before they begin CCBT.

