#### **Primary outcome variable(s)**

Aim 1: 1a) resting state functional connectivity 1b) emotional conflict task-induced brain activity Aim 2 Treatment effects: 2a) amygdala-connectivity 2b) changes rostral/dorsal ACC, DLPFC and IFC activation during the emotional conflict task. Patients will serve as their own controls pre-post treatment. In addition, patients who wait longer for treatment (3-4 weeks) will be compared in a second scan with those who receive immediate treatment (1-2 weeks).

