### **Accrual**

The MDD participants will be primarily recruited from the Outpatient Clinics of the University of Pennsylvania, including the Mood and Anxiety Disorders program, student health and the general adult psychiatry programs. These programs see 400+ new patients with depressive disorders each year and contributed 72 unmedicated MDD participants across 30 months to the recently completed noninferiority study of CCBT. Should the need arise, we also can recruit from the Philadelphia VA Medical Centers Behavioral Health Laboratory (PVAMC-BHL). As the BHL continuously screens from the primary care clinical population of the PVAMC, it will serve as a rich secondary recruitment resource for individuals for this study. As an example, from August 2013 to August 2014, 1,298 individuals between ages 18 and 45 completed assessments within the BHL. Of the 1,194 individuals who completed full assessments, approximately 29.4% screened positive for MDD, providing an ample participant base from which to recruit. We thus anticipate no difficulty enrolling depressed patients into this study. Up to 120 participants will be consented for participation; however we anticipate that approximately 10% will screen fail and another 10% will either drop out during the study or have unusable scanner data; therefore, we aim to have 60 participants with MDD and 40 healthy control participants who complete the entire study with usable data. C.10.1 Power Analysis For Aim 1, based on our pilot data, we assume that DLPFC in HC is positively correlated with amygdala with correlation of  $r=0.1$ , while in contrast it is negatively correlated in MDD with correlation  $r=-0.1$  (standard deviation 0.07). Similarly, our pilot data indicates that IFC in MDD is 70% less correlated with the amygdala than in HC (standard deviation 0.07). Given 60 MDD patients and 40 HC at baseline, we have excellent power (80%) to detect the differences between MDD and HC for their baseline amygdala connectivity in DLPFC and IFC. For subgroup analysis in subjects of each sex separately, we will also have 80% power to detect differences between MDD and HC. Similarly, for baseline task measures, the pilot data indicate up to two-fold higher activation in HC in the four targeted regions (ACC, DLPFC, IFC), indicating that will also have 80% power to detect such differences between MDD and HC (in males and females separately, as well as combining sexes) at the 95% confidence level adjusting for the number of tests. For Aim 2, based on our pilot data, the correlation between IFC and amygdala will increase by 0.09 after CCBT (standard deviation 0.05), and the correlation between precuneus and amygdala will decrease by 0.08 (standard deviation 0.04). We will have 80% power to identify treatment effects comparing the data from 30 MDD patients receiving CCBT in 1-2 weeks with untreated data from the subjects receiving CCBT in 3-4 weeks. We will also have 80% power to detect different treatment effects in males and females separately. For longitudinal changes in activation, we

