which we will also conduct for comparison. Aim 1b: To assess baseline differences between MDD and HC in Emotional Conflict task-induced activation in the dorsal ACC, DLPFC, and IFC, we will apply two approaches: First, perform the voxel-wise general linear model to detect group differences on the AHIF-AHIN contrast; Secondly, we will conduct brain-wide fPCR to explore variations that are associated with depression symptoms while controlling the anxiety symptoms. All analyses will be adjusted for age and sex, and corrected for multiple comparisons by controlling the false discovery rate. Aim 2: Aim 2a: To assess the effect of CCBT on the functional connectome, we will test for differences in amygdala-connectivity between MDD patients who receive treatment immediately (within 1-2 weeks of screening) and those who receive treatment later (within 3-4 weeks of screening). We will examine deficits identified in Aim 1 to compare the MDD groups treated immediately (1-2 weeks) vs. treated later (3-4 weeks) for changes in these regions, adjusting for motion, age and gender. We will also conduct a whole-brain feature search through structured functional principal component analysis (SFPCA) [87]. SFPCA incorporates the longitudinal design complexity and models variation in amygdala-connectivity induced by CCBT through dimension-reduced principal components that are associated with longitudinal changes. Instead of generating contrasts for each hypothesis, it utilizes all available data by explicitly modeling the correlation structures among the observed connectivity maps. Aim 2b: To assess changes of the conflict task-induced activity in ACC, DLPFC, and IFC, we will use the same techniques of SFPCA and targeted mixed-effects modeling adjusting for age and sex. We will also investigate the correlation between the patterns of treatment-induced connectivity and activation normalization. Further, we will investigate the dose-response relationship between total time engaged in CCBT and changes in brain connectivity and activity. Exploratory Aim: We will first use PCR to predict treatment response after CCBT using the baseline amygdala-connectivity map. To avoid overfitting, we will evaluate the prediction performance using bootstrapped cross-validation by iteratively applying learning predictive patterns to 90% of the subjects and testing on the remaining 10%. We will assess treatment response using continuous score changes in depression and anxiety, and remission status (defined by MADRS10 after CCBT). For continuous measures of response, we will assess predicted mean-square error (MSE) for symptomatic change in two ways: first, we will simply estimate the predictive performance of the principal scores. Next, we will compare a predictive model based on regression with only baseline depression scores to a model with both baseline scores and principal scores to assess the added value of the imaging markers. For remission status, we will assess both the predictive performance of the principal scores and the added value of these markers above baseline depression scores and other demographics (age, sex, socio-economic status) using receiver-operator characteristic (ROC) curve analysis. Differences in the performance will be assessed by building confidence intervals for increased area under the curve (AUC) using bootstrapped cross-validation. We will apply the same techniques to the contrast of parameter maps from the conflict task, as well as to the cortical thickness maps. We will build second stage meta-classifiers that integrate the patterns found using these functional and structural imaging measures using generalized linear modeling, which will allow us to integrate the imaging predictors with age, sex, and other demographic information. To assess the importance of baseline executive function measures, we will examine the improvement in predictive performance by including these into the meta-classifiers. Other machine learning algorithms such as support vector machines and random forests, as well as collaborative learning will also be explored to achieve optimal performance. We will also assess the amount of model improvement by incorporating joint resting-state, task-based activation, and cortical thickness patterns into the previous PCR model by calculating c-statistics and prediction indices (such as net reclassification improvement and integrated discrimination improvement etc.) sequentially. Finally, we will investigate sparse patterns of association between imaging measures and depression phenotypic measures using sparse canonical correlation analysis. \*\*\*NOTE REGARDING DATA ANALYSIS WITH PROTOCOL 826910\*\*\* Procedures and data elements are the same between #826910 and #832295, therefore they will not need to be reconciled. The data from the two study will be added together. Participant data from the Immediate CCBT group from #826910 and the early CCBT group from #832295 will be grouped together for analysis. Participant data from the Wait-list Followed by CCBT group from #826910 and the delayed CCBT group in #832295 will be grouped together for analysis.

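### The targeted Aim 2a Early-versus-Later comparison of change leaves out the same region's scan-1 value; adding it costs one degree of freedom and may narrow the interval modestly, though the gain could be nil

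*Combined protocol and SAP*

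**What the plan says.** Analysis Plan, Aim 2a, takes the regions found abnormal in Aim 1 and compares patients treated immediately with those "treated later (3-4 weeks) for changes in these regions, adjusting for motion, age and gender". It names no model for this step. A whole-brain search by structured functional principal component analysis (SFPCA) follows as an additional analysis. Targeted mixed-effects modelling is mentioned only under Aim 2b, with age and sex as covariates. Nowhere in Aim 2 is the region's scan-1 value a covariate, and nowhere are the two arms given a common scan-1 mean.

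Scan 1 is available for everyone. The Abstract states: "All subjects will have an fMRI at baseline; MDD subjects will have an fMRI after treatment".

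The comparison is secondary in order but distinct in kind. Primary outcome variable(s) reads: "Patients will serve as their own controls pre-post treatment. In addition, patients who wait longer for treatment", and goes on to a second-scan comparison with the patients treated immediately.

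The power analysis under Accrual supplies the only variability figures:
- Aim 1: "IFC in MDD is 70% less correlated with the amygdala than in HC (standard deviation 0.07". The same SD is given for the DLPFC.
- Aim 2, IFC: "the correlation between IFC and amygdala will increase by 0.09 after CCBT (standard deviation 0.05".
- Aim 2, precuneus: "the correlation between precuneus and amygdala will decrease by 0.08 (standard deviation 0.04".
- Aim 2 contrast: 80% power, "comparing the data from 30 MDD patients receiving CCBT in 1-2 weeks with untreated data from the subjects receiving CCBT in 3-4 weeks".

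On allocation, Design, Procedures and Risk / Benefit Assessment describe random assignment to Early or Later CCBT. The Abstract says "MDD subjects will be scheduled to receive CCBT at the first available appointment", and the Protocol Description under Basic Info is similar.

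**The concern.** A change score is a scan-1-adjusted analysis with the slope on scan 1 fixed at 1. If the true slope is below 1, as it is when the two scans vary equally and are imperfectly correlated, the fixed slope carries avoidable noise into the group comparison. Under random allocation, estimating the slope removes that noise without changing the quantity being estimated.

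Early versus Later is the plan's only comparison of treated with untreated depressed patients. The pre-post comparison cannot separate CCBT from the passage of time. At stake is a somewhat narrower interval for that contrast, and a little more power if the true effects are well below the pilot's. No planned conclusion depends on it.

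**Working it through.** **Inputs.** The SDs are those quoted from Accrual. Arms are 30 v 30 (60 MDD patients, half in each arm). Alpha is taken as two-sided 0.05; the plan states no sidedness. Assumptions: 0.05 and 0.04 are SDs of change; 0.07 is the single-scan SD, borrowed for the precuneus.

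**The plan's power figure.** Standardised effects are 0.09/0.05 = 1.8 and 0.08/0.04 = 2.0. At 30 v 30 both give power above 0.999, so the stated 80% is not reproduced and fits only as a floor. An 80% figure would need an SD of about 0.124 (IFC) or 0.111 (precuneus). This does not affect the present point, except to show that power is ample without the covariate.

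**Correlation implied by the SDs, equal scan variances.** SDchange² = 2s²(1 − ρ), so ρ = 1 − SDchange²/(2 × 0.07²).
- IFC: 1 − 0.0025/0.0098 = 0.745
- Precuneus: 1 − 0.0016/0.0098 = 0.837

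**Gain before cost.** The variance of change is 2s²(1 − ρ). After scan-1 adjustment it is s²(1 − ρ²). The ratio is (1 + ρ)/2, so interval width is multiplied by √((1 + ρ)/2).
- IFC: √0.872 = 0.934
- Precuneus: √0.918 = 0.958

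**Cost of the extra covariate, N = 60.** √(1 + 1/56) × t(57)/t(58) = 1.0089 × 1.0004 = 1.0093.

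**Net interval width.**
- IFC: 0.934 × 1.0093 = 0.943, or 5.7% narrower. The half-width goes from 0.0258 to 0.0244.
- Precuneus: 0.958 × 1.0093 = 0.967, or 3.3% narrower. The half-width goes from 0.0207 to 0.0200.

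With motion, age and sex also in the model the figures are 5.7% and 3.2%, and a simulation with those covariates agrees.

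**Sensitivity to equal variances.** Keep the scan-1 SD at 0.07 and the SD of change as given, and let the scan-2 SD be s₂. Then ρ = (0.07² + s₂² − SDchange²)/(2 × 0.07 × s₂), and width is multiplied by s₂√(1 − ρ²)/SDchange × 1.0093.

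| Scan-2 SD | IFC, net gain | Precuneus, net gain |
|---|---|---|
| 0.060 | 15.2% | 13.7% |
| 0.070 | 5.7% | 3.3% |
| 0.075 | 2.4% | 0.3% |
| 0.080 | 0.1% | −0.9% |

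With the planned covariates also counted, the last precuneus entry is −1.0%. The gain vanishes because the slope of scan 2 on scan 1 approaches 1. For the IFC at 0.080 it is 0.786 × 0.08/0.07 = 0.90.

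**Power.** At half the IFC pilot effect (d = 0.9, an assumption), 30 per arm and ρ = 0.745, power goes from 0.93 to 0.95.

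**The case against.** The strongest reply is that nothing is wrong: the change-score comparison is valid under randomisation, power is near 1 at the pilot effects, and the pre-post comparison comes first. That stands, and it limits this to a suggestion.

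A second reply is that the sentence names no model, so scan 1 might yet be handled. Aim 2b's wording hints at mixed models, and SFPCA uses the correlation between scans. This stands in part. But the covariate list is explicit, and SFPCA is a separate whole-brain search. With two complete scans and free arm means at each, a mixed model gives the same group contrast as a change score. Later patients have a third scan and the parameterisation is unstated, so that equivalence cannot be asserted for every model the team might fit.

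A third reply is that the size is inferred from SDs whose meaning the power analysis does not define. This stands, and it is why the gain is given as a range that includes zero.

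A reader might infer that the unadjusted comparison is biased or underpowered. The documents support neither: random assignment is stated in three places, and the plan's own effects and SDs give power above 0.99.

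A reader might also infer that, because allocation is unclear for some patients, the main analysis should use only the 37 MDD patients of protocol 832295. That does not follow. Dropping the other 23 (60 − 37, from Target population) would widen intervals by about √(60/37) = 1.27, or 27%, which outweighs the covariate's gain. How the 826910 patients were allocated is a separate question that these documents cannot answer.

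**Conclusion.** The omission is real, and its effect is small and uncertain. Under random assignment the planned analysis is valid, and the loss is one of precision only. On the plan's own SDs, adding the scan-1 value narrows the 95% interval by about 6% (IFC) and 3% (precuneus) at 30 per arm. That rests on three readings: 0.05 and 0.04 are SDs of change, 0.07 applies to a single scan in both regions, and the two scans vary equally. If the scan-2 SD is 0.08 instead, the result runs from a 0.1% gain to a loss of about 1%; if it is 0.06, the gain is about 14-15%.

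The figures are also approximate because the arms' scan intervals differ. The Early arm's second scan is at CCBT Week 9, while the Later arm's is two to four weeks after the first, so one shared correlation may not hold. Adjustment does not correct that difference.

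The argument depends on random allocation. If some patients were allocated otherwise, the adjusted and unadjusted analyses would target different quantities and the covariate could not be called a near-free gain. This is worth considering; it is not a defect that threatens a conclusion.

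**What to change.** In the Analysis Plan, Aim 2a, state that for each targeted region the second-scan value (or the change) will be modelled on arm, with that region's scan-1 value as a covariate alongside motion, age and sex. The cost is one sentence, a measurement already collected and one degree of freedom. That raises the variance by about 1.8% at 30 per arm, already counted in the net figures.

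Separately, reconcile the first-available scheduling in the Abstract and Basic Info with the random assignment in Design, Procedures and Risk / Benefit Assessment, and state how the patients pooled from protocol 826910 were allocated. The precision argument needs that statement. Restricting the main analysis to protocol 832295 is not part of this change.

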### ***Objectives***

#### **Overall objectives**

The overall objectives of the study are to examine novel potential neural circuit bio-markers of treatment response to computer-augmented cognitive behavioral therapy (CCBT) for people with MDD. Aim 1: Compare baseline resting state functional connectivity and task-induced activity between MDD and controls: Hypothesis 1a): Compared with controls, depressed participants will have disruptions in resting state functional connectivity in the amygdala-cognitive-executive (C-E) network and the amygdala-default mode network (DMN); and 1b) will have decreased emotional conflict task-induced activation in rostral/dorsal anterior cingulate cortex (ACC), dorsal lateral prefrontal cortex (DLPFC), and inferior frontal gyrus (IFG). Aim 2: Assess CCBT treatment effects on resting state functional connectivity and task induced activity in MDD comparing post-CCBT treatment to pre-CCBT treatment. Hypothesis 2a) Compared with pre-CCBT neuroimaging measures, following active treatment there will be increase in C-E connectivity and decreased amygdala-DMN connectivity. 2b) These changes will be correlated with symptom reduction and 2c) increases in rostral/dorsal ACC, DLPFC and IFG activation during the emotional conflict task. Exploratory Aim: 1a) Predict the effects of baseline brain measures on treatment outcomes. Hypothesis: Using clinical decision-support algorithms, clinical outcome trajectories and differential response to treatment will be predicted from baseline data (brain connectivity, task-based activity and cortical thickness). 1b) Predict the effects of baseline executive function on treatment outcomes. Hypothesis: Using clinical decision-support algorithms, clinical outcome trajectories and differential response to treatment will be predicted from baseline executive function data. Developing such algorithms to help determine risk trajectories is important for more effective treatment assignment. Secondary Aims: Data collected from actigraphy, saliva sample, and remote monitoring via the Beivei cellphone application will be used as preliminary evidence examining the effects of sleep-wake patterns, microbiome, and total physical activity on treatment outcomes in individuals experiencing depression.

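### Exploratory hypothesis 1b concerns executive function's own prediction of outcome, but the plan specifies only its increment over imaging meta-classifiers

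*Combined protocol and SAP*

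**What the plan says.** Under Overall objectives, the Exploratory Aim has two parts. Part 1a concerns baseline brain measures. Part 1b is separate: "1b) Predict the effects of baseline executive function on treatment outcomes". Its hypothesis is that "clinical outcome trajectories and differential response to treatment will be predicted from baseline executive function data". Nothing in that wording makes the prediction conditional on imaging.

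In the Analysis Plan (C.10, Exploratory Aim), executive function appears in one sentence: "To assess the importance of baseline executive function measures, we will examine the improvement in predictive performance by including these into the meta-classifiers". The models it is added to are described just before: "We will build second stage meta-classifiers that integrate the patterns found using these functional and structural imaging measures using generalized linear modeling", together with age, sex and other demographic information.

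Imaging is treated more fully in the same section. For continuous symptom change, the plan says "first, we will simply estimate the predictive performance of the principal scores", and then compares a model holding only baseline depression scores with "a model with both baseline scores and principal scores to assess the added value of the imaging markers". For remission, "we will assess both the predictive performance of the principal scores and the added value of these markers above baseline depression scores" and demographics, by ROC analysis. The same techniques are extended to the task contrast maps and the cortical thickness maps. Neither step is specified for executive function.

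**The concern.** The hypothesis and the analysis address different quantities. Hypothesis 1b is about the predictive value of executive function. The planned comparison is about its value given connectivity, task activation, cortical thickness and demographics. The two coincide only in special cases, such as when executive function is uncorrelated with everything already in the model.

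Overlap is plausible on the protocol's own reasoning. Potential Study Benefits describes the expected mechanism of CCBT as stronger cognitive and executive control over limbic-frontal circuits, and the cognitive-executive network is a target in Aims 1 and 2. If the imaging scores and the executive-function measures partly reflect the same process, adding executive function to a model that already holds imaging credits the shared signal to imaging.

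At stake is the interpretation of 1b. With a small or null increment, the investigators could not tell a measure that does not predict outcome from one that predicts it through information the scans also carry.

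**Working it through.** **Is there a figure to reproduce?** No. The power analysis under Accrual covers Aims 1 and 2 only. The documents give no effect size, performance target or sample size for 1b, and no correlation between executive function and the imaging scores. All correlations below are therefore assumptions.

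**Step 1. What is specified for each predictor (Analysis Plan, Exploratory Aim).**

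| Analysis | Imaging | Executive function |
|---|---|---|
| Performance alone | specified | not specified |
| Added value over baseline depression score | specified | not specified |
| Added value over the other predictor set | not specified | specified |

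The neighbouring sentences do not fill the gap. The other machine-learning methods are listed as a search for best performance, with no model based on executive function alone. The sequential c-statistic step concerns imaging patterns. The sparse canonical correlation links imaging to depression phenotypes.

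**Step 2. Increment against stand-alone value, equal predictors.** Let each predictor explain 10% of outcome variance, with correlation c between them and both related to outcome in the same direction.

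Joint R² = (0.2 − 0.2c)/(1 − c²) = 0.2/(1 + c); increment = joint R² − 0.10.

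| c | Joint R² | Increment (points) | Stand-alone (points) |
|---|---|---|---|
| −0.3 | 0.286 | 18.6 | 10 |
| 0 | 0.200 | 10.0 | 10 |
| 0.3 | 0.154 | 5.4 | 10 |
| 0.5 | 0.133 | 3.3 | 10 |
| 0.7 | 0.118 | 1.8 | 10 |

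**Step 3. Unequal predictors at the planned size.** Take N = 60 (the target for MDD completers with usable data, under Accrual), executive function–outcome r = 0.4, imaging–outcome r = 0.5, and two-sided alpha 0.05 (assumed).

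Increment = (r_EF − r_img·ρ)²/(1 − ρ²). For ρ = 0.3: (0.4 − 0.15)²/0.91 = 0.0625/0.91 = 0.069.

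Power comes from a 1-df noncentral F test with noncentrality N × increment/(1 − full-model R²). Stand-alone R² is 0.160, with power 91%.

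| ρ | Increment in R² | Power for increment |
|---|---|---|
| −0.3 | 0.332 | about 100% |
| 0 | 0.160 | 98% |
| 0.3 | 0.069 | 68% |
| 0.5 | 0.030 | 34% |

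**Step 4. Out-of-sample check.** This used 1,000 simulated data sets per ρ, N = 60, 10-fold cross-validation (90/10, as an approximation to the planned scheme), the Step 3 correlations, and nine imaging scores of which one is informative. Cross-validated R² for executive function alone was 0.13 to 0.14 at every ρ. The gain from adding it to the imaging model was 0.380 at ρ = −0.3, 0.168 at 0, 0.068 at 0.3 and 0.013 at 0.5.

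In Steps 3 and 4 the stand-alone value of executive function is fixed by assumption. Only the planned quantity moves, and it moves in both directions.

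**The case against.** The study is about neural circuit biomarkers, and within that purpose it is legitimate to ask whether executive function improves an imaging model. The aim is exploratory, with no threshold or success criterion for 1b, so nothing in the plan says that a null increment would be declared a failed hypothesis. Both points stand. They limit the consequence to interpretation, but they do not make the increment the quantity that 1b names.

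A reader might also infer three stronger claims, and the documents do not support them:

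- *That 1b is never tested.* A clear positive increment would show that executive function carries predictive information beyond imaging and demographics, which supports 1b. What is missing is a stand-alone test and an interpretable null.
- *That the plan necessarily understates executive function.* This needs a positive overlap, whose size the documents do not give. At zero correlation nothing is lost, and at a negative correlation the increment exceeds the stand-alone value. The executive-control rationale makes understatement plausible, not certain.
- *That a cheap test is being passed over for an expensive scan.* The documents make no cost comparison, and the procedures text mentions only neuropsychological testing. The point does not rest on cost.

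Nor does the plan say that executive function may enter only after imaging. Other orders are left unspecified, not ruled out.

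**Conclusion.** The mismatch holds: 1b is stated unconditionally, and its only specified analysis is conditional on imaging and demographics. Followed as written, the plan estimates the increment of executive function over imaging, and a null increment would not show that executive function fails to predict outcome.

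The numerical effect cannot be fixed from the documents. Under the assumed case of two predictors at 10% each, the increment is 1.8 to 5.4 points for correlations of 0.7 down to 0.3, the full 10 points at zero, and more than 10 when the correlation is negative. That the difference exists does not depend on these values; its direction and size do.

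The change is worth making because it lets the trial answer its own stated question. It bears on one exploratory aim only; no primary outcome or sample-size statement depends on it.

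**What to change.** In the Exploratory Aim of the Analysis Plan, prespecify five models. Fit them in the same bootstrapped cross-validation, on the same folds, with the metrics already planned for imaging (MSE for continuous change, AUC for remission):

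1. executive function alone;
2. benchmark: baseline depression score plus demographics;
3. benchmark + executive function;
4. benchmark + imaging;
5. benchmark + executive function + imaging.

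Judge 1b on model 1 and on model 3 against model 2. Keep the planned increment as a further step, model 5 against model 4. Model 5 against model 3, which shows what imaging adds after executive function, may also be reported. Name the executive-function measures in the analysis text unless the attached assessment schedules, which were not available here, already do so.

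The cost is a few extra fits on data already being collected and a short addition to the plan. The downside is a few more exploratory comparisons on about 60 treated patients, so results should be given as estimates with intervals and labelled exploratory. Current Status of Study reports 4 subjects enrolled under this protocol, so the models can still be set down before most of its data exist. Because data from protocol 826910 will be pooled, this should also be done before any of those outcomes are examined against executive function.

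### Exploratory Aim: the single 90/10 cross-validation layer scores each prediction model but does not cover the choice among models

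*Combined protocol and SAP*

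**What the plan says.** All of this is in the Exploratory Aim part of the Analysis Plan, apart from the sample size.

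- **Validation.** As a stated guard against overfitting of the PCR model, the plan will "evaluate the prediction performance using bootstrapped cross-validation by iteratively applying learning predictive patterns to 90% of the subjects and testing on the remaining 10" percent.
- **Other maps.** "We will apply the same techniques to the contrast of parameter maps from the conflict task, as well as to the cortical thickness maps".
- **Added value for remission.** The comparator is baseline depression score plus age, sex and socio-economic status. "Differences in the performance will be assessed by building confidence intervals for increased area under the curve (AUC) using bootstrapped cross-validation".
- **Second stage.** "We will build second stage meta-classifiers that integrate the patterns found using these functional and structural imaging measures using generalized linear modeling".
- **Further algorithms.** Support vector machines and random forests, "as well as collaborative learning will also be explored to achieve optimal performance".
- **Sequential indices.** Model improvement is also assessed by "incorporating joint resting-state, task-based activation, and cortical thickness patterns into the previous PCR model by calculating c-statistics and prediction indices", with net reclassification improvement (NRI) and integrated discrimination improvement (IDI) as examples. That sentence names no validation.
- **Sample.** Under Accrual, "we aim to have 60 participants with MDD and 40 healthy control participants who complete the entire study with usable data". Only the MDD patients are treated, so prediction of response rests on about 60 people.

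The documents state no selection rule, inner loop, separate hold-out set or optimism correction. They give no remission rate, number of candidate models or number of components.

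**The concern.** Cross-validation gives a fair score for a model fixed in advance. It does not give a fair score for the highest of several models compared on the same held-out predictions, because the winner is partly the model that chance favoured. With 60 patients each 10% test set holds 6 people, so chance has ample room.

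The plan sets optimal performance as the object of its search and gives no step that accounts for the search. At stake is whether imaging predicts response, and whether it adds anything to baseline depression score and demographics. The Overall objectives describe such algorithms as important for treatment assignment, so an inflated AUC could make a chance pattern look like a biomarker worth pursuing.

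**Working it through.** The plan gives no AUC, power or model count for this aim, so there is no figure to reproduce. The check asks how large the optimism could be.

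**Inputs.** From the documents: n = 60, 90/10 splits, three kinds of map, and the named model types. Assumed: 18, 24 or 30 remitters (30%, 40%, 50%), 80 features per map, between-map correlation 0.3, and 3 principal scores per map.

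**1. Hand check.** With no signal, the standard error of an AUC is approximately √[(n₁ + n₀ + 1) / (12 n₁ n₀)].

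- 18 remitters: √[61 / (12 × 18 × 42)] = 0.082
- 24 remitters: √[61 / (12 × 24 × 36)] = 0.077
- 30 remitters: √[61 / (12 × 30 × 30)] = 0.075

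The largest of six independent standard normal values averages 1.267. The best of six useless models would therefore average about 0.5 + 1.267 × 0.077 = 0.60 (0.60 at all three rates after rounding). This is only a rough guide, since real candidates are correlated and cross-validated AUCs do not follow this formula exactly.

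**2. Null simulation.** The six candidates are PCR on each of three maps, a generalised linear model on the scores of all three, and a support vector machine and a random forest on the joined maps. Collaborative learning is left out because the plan does not specify it. There were 150 replicates per remission rate, or 50 for nested selection (inner 5-fold). The true AUC is 0.50.

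| Reported figure | 18 remitters | 24 | 30 |
|---|---|---|---|
| PCR on one map, fixed in advance | 0.470 | 0.470 | 0.499 |
| Best of 6, own cross-validated score | 0.587 | 0.582 | 0.592 |
| Best of 6, chosen inside the training 90% | 0.494 | 0.494 | 0.481 |

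The best-of-6 score exceeded 0.60 in 39%, 41% and 44% of null trials, against 8 to 12% with nested selection. The 0.60 mark is descriptive and is not a threshold in the plan.

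A separate null run of the best of six gave 0.59 to 0.60, against 0.48 to 0.49 for fixed PCR and 0.50 to 0.51 nested. A further run used 16 candidates with stand-in algorithms and averaged each score over three repeats of cross-validation. It gave 0.61 to 0.62, so repeating the splits did not remove the effect. Nested selection in that setting gave 0.500 (standard error 0.014).

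**3. Gain over baseline.** This is closer to the plan's own added-value measure. Null maps were added to a baseline score and three noise covariates, and the best of six cross-validated AUC gains was taken (200 replicates per setting, kernel ridge standing in for the support vector machine and forest).

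- Predictive baseline score (cross-validated AUC 0.65 to 0.68): mean false gain +0.02 to +0.03; 14 to 23% of trials exceeded 0.05.
- Uninformative baseline score: mean false gain +0.09; 58 to 62% exceeded 0.05.

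**4. Strong real signal.** Best-of-6 reported AUC minus the same model's AUC on 3,000 new subjects:

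- 18 remitters: 0.747 − 0.728 = 0.019
- 24 remitters: 0.745 − 0.739 = 0.006
- 30 remitters: 0.744 − 0.737 = 0.007

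**The case against.** The strongest reply has four parts.

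**The plan already commits to cross-validation.** The aim opens with it, extends it to the other maps, and names it again for the AUC gain. This disposes of most of the worry about the sequential indices. A reader might infer from the sentence on the c-statistic, NRI and IDI that they will be computed on the fitting data, where they rise even when pure noise is added. The documents do not support that reading. For remission the c-statistic is the AUC, whose gain is already cross-validated; the sentence extends the PCR model that is under that scheme; and in-sample figures would defeat the stated purpose. What remains is missing detail on these indices and on how first-stage scores enter the meta-classifiers. The reply does not reach selection: even if the 90/10 layer covers every model, it does not cover the choice among them.

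**No winner is promised.** A reader might also infer that only the best model will be reported. The plan does not say so. It names PCR first, and its meta-classifiers combine maps and do not set them against each other. The harm is therefore conditional on how results are reported. It is not idle, because the search is described as a search for performance and the reporting is left open.

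**Raw AUC is not the plan's added-value test.** This stands. The gain over baseline is smaller when the baseline score predicts, and the plan's confidence interval for that gain was not simulated. Larger inflation can be produced by crossing every learner with every map, but the plan does not describe that grid.

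**The aim is exploratory.** This also stands and sets the severity.

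**Conclusion.** The concern holds as a minor point. One cross-validation layer evaluates models but not selection among them, and on about 60 patients that matters when the signal is weak or absent. If the best model's own score is what gets reported, useless models would show an average AUC of about 0.58 to 0.60 where nested selection gives about 0.50. The false gain over baseline would be about 0.02 to 0.03 with a predictive baseline score and about 0.09 with an uninformative one. With a strong real signal the overstatement is 0.01 to 0.02.

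These sizes rest on assumed remission rates, candidate counts, feature counts and map correlation, and on plain 10-fold splitting in place of the plan's bootstrapped scheme. They show direction and rough scale. Only remission was simulated. The same reasoning applies to mean-square error for continuous score change, but its size was not calculated. Aims 1 and 2 are unaffected, and no decision in the documents depends on these models.

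**What to change.** Add to the Exploratory Aim:

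1. Modality, algorithm, tuning and number of components are chosen in an inner loop within each training 90%, and performance is reported from the outer 10%.
2. The PCR amygdala-connectivity model is reported whatever its result, with a list of all models tried.

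As a clarification only, state that meta-classifiers receive out-of-fold first-stage scores, and that the sequential c-statistic, NRI and IDI use the same held-out predictions.

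The cost is more computing time and probably less favourable performance figures. No new data or visits are needed.
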